3.4 Permitted and Restricted Concomitant Medications/Treatments

All prescription, non-prescription, or over-the-counter medications including herbal remedies, dietary and nutritional supplements and complementary and alternative therapies given to, or taken by the patient at study entry (including Screening) and during the study must be clearly documented on the case report form (CRF).

Any medication considered necessary for the patient's safety and well-being may be given at the discretion of the Investigator(s).

For treatment of DLT or any other clinically significant events, any available standard therapy may be used as required.

Prohibited treatments are summarized below:

- other antineoplastic agents;
- concurrent radiation treatment will be permitted during this study for symptom control;
- other investigational medicinal products.

3.5 Study Analysis Populations

Enrolled Patients: All patients who enroll in the trial.

Efficacy Population: All patients with at least one post-baseline tumour response assessment

Safety Population: All patients who receive at least one dose of study drug.

3.6 Withdrawn Patients

3.6.1 Patient Withdrawal or Discontinuation

Patients may withdraw from the study at any time without stating a reason and without prejudice to further treatment. A Final Study Visit should be performed 30 +/-3 days after the last dose of ALM201 to enable follow up safety assessments and further tumour assessment where required.

The Investigator may withdraw a patient from the study and discontinue study treatment and assessments at any time. Example reasons for discontinuing a patient from this study are:

- Disease progression.
- The patient experiences a toxicity, including those necessitating a dose delay of >14 days (See Protocol Section 4.2.1), where the re-introduction of ALM201 (including a dose reduction of ALM201), is not considered suitable. Exceptions may be considered where the toxicity is not considered to be ALM201 treatment-related.

TPBS001 Version 6 (based on TPQA036 Version 2)

CONFIDENTIAL

| Sponsor: Almac Protocol Number: ALM201/0001 | Sponsor: | Almac | Protocol Number: | ALM201/0001 |
|---|----------|-------|------------------|-------------|
|---|----------|-------|------------------|-------------|

• Other toxicities or events, unrelated to ALM201, that would, in the Investigator's opinion, prevent the patient from continuing on this trial.

- Protocol non-compliance. (All documentation concerning the patient must be as complete as possible. Withdrawals due to non-attendance of study visits must be followed-up by the Investigator to obtain the reason for where possible).
- Patient withdraws consent to participate in the study.
- Patient becomes pregnant (see Protocol, section 7.4.3)

The Sponsor reserves the right to request the withdrawal of a patient due to protocol violation or other significant reason. Patients who experience a toxicity event which qualifies as a DLT, may continue to receive ALM201 if considered safe to do so and where continued treatment is considered by the Investigator to be in the patient's best interests. The decision to continue treatment will be reviewed by the CRC (See Protocol Section 8.1) and will involve an adjustment (de-escalation) in dose or dose schedule.

3.6.2 Replacement of Non-evaluable Patients

In Part 1, patients will be replaced if they are not considered evaluable for DLT during Cycle 1. As a general rule during Part 1, patients will be considered evaluable for DLT during Cycle 1 if they receive at least 80% (i.e. 12 of 15 planned doses) of their intended dose, unless this is due to ALM201-related toxicity. However, this will be reviewed by the CRC on a case-by-case basis. For example, based on safety and PK data available, the CRC may agree that on a weekday dosing schedule, missing 1 dose per week on the 21-day dosing cycle is acceptable; whereas, missing 3 consecutive doses is not. Furthermore, the ability to evaluate a patient who misses more than 80% of their intended dose due to toxicity considered to be related to ALM201, but which is not ultimately classed as a DLT, will be reviewed on a case-by-case basis. Patients who withdraw from the study or discontinue treatment after completion of the first treatment cycle will not be replaced.

3.7 Sample Size

No formal sample size calculation was performed.

CONFIDENTIAL

4 Statistical Methodology

4.1 Analysis Conventions

This section details general conventions to be used for the statistical analyses. Departures from these general conventions may be given in the specific detailed sections of this analysis plan. All data were collected using electronic case report forms (eCRFs).

- For all analyses, each dose level and overall will be summarized using descriptive summary statistics. Each treatment group will have a cohort number and data will be summarized in all tables, listings, and figures by treatment or cohort number. No statistical comparison of dose levels will be performed.
- Summary statistics will consist of the number and percentage for categorical variables, and the number of observations (n), mean, standard deviation (Sd), minimum, median, and maximum values for continuous variables. When the standard deviation cannot be calculated, a hyphen (-) will be used.
- All mean and median values will be formatted to one more decimal place than the
 measured value on the eCRF. Standard deviation values will be formatted to two more
 decimal places than the measured value on the eCRF. Minimum and maximum values
 will be presented with the same number of decimal places as the measured value on the
 eCRF.
- The number and percentages will be presented in the form XX (XX) where the percentage is in the parentheses. Unless otherwise specified, the denominator for percentages will be the number of patients in a given dose level within the analysis population of interest.
- All summary tables will include the analysis set sample size (i.e., number of patients).
- Baseline is defined as the last planned assessment before the first administration of study drug, unless otherwise specified. Typically this will be the Cycle 1 Day.
- Change from baseline will be calculated as follows:

Change from baseline = Post-baseline value – baseline value.

- Age will be calculated as the integer: (Date of informed consent date of birth)/365.25, rounded down to the nearest integer.
- Duration of time on study drug (days) = Date of last injection date of first injection+1.
- Date and time variables will be formatted as DDMMMYYYY hh:mm for presentation.

TPBS001 Version 6 (based on TPQA036 Version 2)

CONFIDENTIAL

| Sponsor: | Almac | Protocol Number: | ALM201/0001 |
|----------|-------|------------------|-------------|
| | | | |

- Summary tables with present data from scheduled assessments; listings will include all data, sorted by date.
- Tables, figures, and listings will be presented in landscape orientation.
- SAS® Version 9.4 or higher will be the statistical software package used for all data analysis.
- AEs and medical history will be coded using the Medical Dictionary for Regulatory Activities (MedDRA) Version 17.0.
- Prior cancer therapies and prior and concomitant medications will be coded using the WHO Drug dictionary version March 2014.
- No imputation of values for missing data will be performed, unless otherwise stated.

4.2 Disposition of Patients

Patient disposition will be summarized with the frequency and percentage of the following items: patients who enrolled (i.e., All Patients), patients who received at least one dose of study drug (i.e., Safety Population), patients who received at least one dose of study drug and completed at least one post-baseline response evaluation (i.e., Efficacy Population), the number of patients dosed at each cycle, patients who discontinued the study and the reasons for discontinuation.

A summary of protocol deviations will be presented. Protocol deviations are defined in Insight as:

- Eligibility
- ICF Issue
- IP Non-compliance
- IP Dispensing Error
- Assessment not performed per protocol
- Failure to adhere to visit schedule
- Other

Patient disposition, protocol deviations, and eligibility criteria (including inclusion/exclusion) will be presented in data listings.

4.3 Baseline and Demographic Characteristics

4.3.1 Demographics and Baseline Characteristics

Demographic and baseline characteristics data will be summarized for all patients in the Safety population. Summary statistics will be calculated for race, ethnicity, gender, age, height (cm), weight (kg), left ventrical ejection fraction (LVEF) and Eastern Cooperative Oncology Group (ECOG) performance status at screening, as well as female reproductive status. Age will be

TPBS001 Version 6 CONFIDENTIAL Effective Date: 15th March 2017 (based on TPQA036 Version 2) Prior Effective Date: 9th October 2016

| Sponsor: | Almac | Protocol Number: | ALM201/0001 |
|---------------|---------|--------------------------|---------------------|
| - OP 0110 011 | , minas | i i oto oo i i tailiboi. | , (E.IVIEO 1, 000 I |

summarized as a continuous and categorical variable (≤ 55 years and > 55 years). All demographic and baseline data will be presented in data listings.

4.3.2 General Medical History

General medical history will be coded using MedDRA Version 17.0 system organ class (SOC) and preferred term (PT). It will be summarized, sorted by alphabetical order of SOC and preferred term. For the table summary, a patient will only be presented once for each level of summarization. Medical history will be presented in a data listing.

4.3.3 Cancer History

Time from date of initial cancer diagnosis to study entry (i.e., informed consent date) (months) and disease-specific characteristics of primary tumour, such as histology and tumour stage will be summarized.

Prior cancer therapies by number of previous regimens, duration of therapy, type of agent (chemo, immunotherapies, hormonal therapy, monoclonal therapy, radiation therapy and others), WHO ATC Level II drug class, and WHO preferred term, reason for administration, best response on therapy, and reason for discontinuation. For radiotherapies, field of radiation and estimated radiation dose will be summarized as well. All cancer history and prior cancer therapies will be presented in data listings.

4.3.4 Prior and Concomitant Medication and Ancillary Procedures

All prescription, non-prescription, or over-the-counter medications including herbal remedies, dietary and nutritional supplements and complementary and alternative therapies will be coded using the WHO Drug dictionary version March 2014 and classified into the default ATC code provided by the system.

A prior medication is defined as any medication started and stopped prior to the first administration of study drug. Concomitant medications are those taken on or after the first dose of study drug.

The incidence of concomitant medications by WHO ATC level II drug class and preferred term will be summarized and presented in alphabetical order of ATC level and preferred term for the Safety population. For the table summary, a patient will only be presented once for each level of summarization.

All medications (prior and concomitant) and any ancillary procedures will be presented in a data listing.

4.4 Exposure

Summary of exposure will include the total number of days on study medication and total dose received, and, by cycle, the location sites of injection, the total amount injected per visit and dose modification details. All study drug exposure information will be presented in a listing.

TPBS001 Version 6 (based on TPQA036 Version 2)

CONFIDENTIAL

4.5 Efficacy / Primary and Secondary Analysis

As this is a phase 1 study, the extent of efficacy data is expected to be limited. However, a summary of Clinical benefit, by RECIST Version 1.1 from patients with evaluable disease will be generated. The summary will include the number and percent of patients, overall and by cohort with:

- Complete response (CR)
- Partial Response (PR)
- Overall Response (CR+PR)
- Stable Disease (SD)
- Disease Control Rate (SD+CR+PR)
- Progressive Disease (PD)
- Not Evaluable

Listings detailing the target, non-target, overall response assessments reported, and survival follow-up will be presented.

4.6 Pharmacokinetic Analysis

This analysis will be described in a separate document and the results presented in a separate document as well.

4.7 Analyses of Safety and Tolerability

All safety analysis will be performed on Safety Population.

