4.7.1 Adverse Events

Adverse events will be summarized in terms of treatment-emergent adverse events (TEAEs) where treatment-emergent is defined as any AE that occurs after administration of the first dose of study drug and through 28 days after the last dose of study drug, any event that is considered study drug-related regardless of the start date of the event, or any event that is present at baseline but worsens in intensity or is subsequently considered study drug-related by the Investigator. Treatment-related TEAEs include those events considered by the investigator to be possibly, probably, or definitely related to study drug.

Adverse Events will be coded using MedDRA version 17.0 and graded according to the National Cancer Institute (NCI) Common Terminology Criteria for Adverse Events (CTCAE) v4.03. The incidence of TEAEs will be summarized by MedDRA System Organ Class (SOC), Preferred Term (PT) and NCI CTCAE grade. Tables summarizing the incidence of TEAEs will be generated for each of the following:

- Treatment Emergent AE Overview;
- All TEAEs by SOC and PT;
- TEAE by SOC, PT, and CTCAE Grade
- Treatment-Related TEAEs by SOC and PT;

TPBS001 Version 6 CONFIDENTIAL Effective Date: 15th March 2017 (based on TPQA036 Version 2) Prior Effective Date: 9th October 2016

| Sponsor: | Almac | Protocol Number: | ALM201/0001 |
|----------|-------|------------------|-------------|

- Treatment-Related TEAEs by SOC, PT and CTCAE grade;
- Treatment Emergent Serious Adverse Events by SOC and PT;
- Treatment Emergent Serious Adverse Events by SOC, PT and CTCAE grade;
- Treatment-Related Treatment Emergent Serious AEs by SOC and PT;
- Treatment-Related Treatment Emergent Serious Adverse Events by SOC, PT and CTCAE grade;
- Treatment-Emergent Adverse Events ≥ Grade 3 by SOC and PT
- Treatment-Related Treatment-Emergent Adverse Events ≥ Grade 3 by SOC and PT
- TEAEs leading to discontinuation of study drug by SOC and PT
- TEAEs leading to modification/interruption of study drug by SOC and PT
- Dose Limiting Toxicities by SOC and PT
- Fatal TEAEs by SOC and PT

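### The DLT table uses the Safety Population, so dosed patients replaced as not DLT-evaluable stay in its denominator and lower any non-zero DLT percentage

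*SAP*

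**What the plan says.** SAP Section 4.7 sets one population for the whole safety section: "All safety analysis will be performed on Safety Population". Section 3.5 defines it: "Safety Population: All patients who receive at least one dose of study drug". The only other sets defined there are the enrolled patients and an efficacy set that needs a post-baseline tumour assessment.

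Section 4.1 supplies the default denominator. Unless something else is specified, "the denominator for percentages will be the number of patients in a given dose level within the analysis population of interest". It also asks for a pooled column: "For all analyses, each dose level and overall will be summarized using descriptive summary statistics".

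Section 4.7.1 lists one DLT output, "Dose Limiting Toxicities by SOC and PT", and gives it no population or denominator of its own.

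On evaluability, SAP Section 3.6.2 says that in Part 1 "patients will be replaced if they are not considered evaluable for DLT during Cycle 1". The general rule is receipt of at least 80% of Cycle 1 doses (12 of 15), unless the shortfall is due to ALM201-related toxicity. The Cohort Review Committee (CRC) reviews this case by case. The protocol synopsis gives the same 80% criterion under Dose Limiting Toxicity and under Cohort Review Committee. It also counts Part 1 in evaluable patients (up to 36 over 6 escalation cohorts) and expands a cohort with a DLT until up to 6 patients can be evaluated.

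**The concern.** The design and the reporting use different sets of patients. For the DLT assessment, a patient who took too few Cycle 1 doses for reasons other than drug toxicity is set aside and another is enrolled. In the table, that same patient is back in the denominator as someone observed without a DLT. Each such patient pulls a non-zero DLT percentage down, at the dose level and in the overall column, relative to the rate in the patients the design regards as informative.

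Cycle 1 DLT is a listed primary endpoint (SAP Section 2.4). The study was halted after Part 1, so this SAP governs the final report of the part in which DLT was assessed. A reader would naturally compare the table's N with the 3 or 6 patients in the MTD rule restated in SAP Section 3.1. Nothing in the table would show how many of that N were evaluable.

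**Working it through.** The plan states no DLT rate, target rate or formal sample size, so there is no figure of its own to reproduce. Two pieces of its arithmetic that bear on the point agree: 0.80 × 15 = 12 doses, and 6 cohorts × 6 patients = 36 evaluable patients.

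**Who is in the denominator.** Consider a Part 1 patient who receives at least one dose, falls short of 80% in Cycle 1 for a reason unrelated to ALM201, has no DLT, and is judged not evaluable.

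- SAP 3.6.2: the patient is replaced.
- SAP 3.5: the patient is in the Safety Population, having been dosed.
- SAP 4.7 and 4.1: the patient counts in the denominator of every safety percentage at that dose level and overall.
- SAP 4.7.1: the DLT table is not exempted.

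Two neighbouring cases are not affected. A replaced patient who was never dosed is outside the Safety Population. A patient whose shortfall was due to ALM201-related toxicity may still count as evaluable.

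**Size.** Let x be the patients with a DLT, n the evaluable patients, and r the dosed, replaced patients without a DLT.

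- Rate in evaluable patients: x / n
- Rate in the table as planned: x / (n + r)
- Ratio of the second to the first: n / (n + r)

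The documents do not give x or r. The values below are assumptions: r = 0, 1 or 2, and x = 1 unless stated. The main case is a cohort expanded to n = 6, because the protocol expands a cohort on its first DLT. The overall column is shown for n = 11 (assumed: five single-patient cohorts plus one expanded to 6, 5 × 1 + 6) and for n = 36 (the protocol's anticipated upper number for the escalation cohorts).

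| Setting | r = 0 | r = 1 | r = 2 |
|---|---|---|---|
| Dose level, n = 6, x = 1 | 1/6 = 16.7% | 1/7 = 14.3% (−2.4 points) | 1/8 = 12.5% (−4.2 points) |
| Dose level, n = 6, x = 2 | 2/6 = 33.3% | 2/7 = 28.6% (−4.8 points) | 2/8 = 25.0% (−8.3 points) |
| Overall, n = 11, x = 1 | 1/11 = 9.1% | 1/12 = 8.3% (−0.8 points) | 1/13 = 7.7% (−1.4 points) |
| Overall, n = 36, x = 1 | 1/36 = 2.78% | 1/37 = 2.70% (−0.08 points) | 1/38 = 2.63% (−0.15 points) |

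In relative terms, at n = 6 one such patient lowers the percentage by 1 − 6/7 = 14.3%, and two lower it by 1 − 6/8 = 25.0%. If x = 0 the result is 0% for every r. If r = 0 this dilution does not arise.

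**The case against.** The strongest reply is that the DLT table sits among tables of adverse event incidence. There, all dosed patients is a coherent denominator that matches the neighbouring tables. No DLT rate, target or interval is promised, no formal analysis is planned for dose escalation, and dose levels are not compared. On this view the Safety Population percentage is a different quantity, correctly labelled, and not a wrong one. It has the merit of not dropping a DLT that occurs in a non-evaluable patient.

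Several parts of this stand. No decision rests on the table: the MTD rule is based on counts, and the CRC decides from its own Cycle 1 review. The effect needs both a DLT and a replaced, dosed, DLT-free patient, and the overall column moves little. Much can be recovered, since N is printed (SAP 4.1), numbers dosed per cycle are summarised (4.2) and exposure is listed (4.4). With cohorts this small, a reader could largely rebuild the 80% criterion.

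Two parts do not stand. First, evaluability is finally a case-by-case CRC judgement, and exposure listings do not record it, so the set that the design used cannot be fully rebuilt. Second, counting unassessable patients as non-events can only lower a toxicity percentage, which is not the cautious direction. A DLT in a non-evaluable patient can be kept visible without keeping the wrong denominator.

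Protocol Section 4.2.1, the CRC Charter and any table shells were not available. A shell footnote giving the number evaluable would ease the problem, but it cannot be assumed to override an explicit rule in the SAP.

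**Conclusion.** The concern holds. As written, the SAP puts dosed patients whom the design excludes from DLT assessment into the denominator of its only DLT table, and any non-zero percentage is lowered by the factor n / (n + r). In the main assumed case (one DLT, 6 evaluable, one or two replacements), 16.7% is shown as 14.3% or 12.5%. The direction is certain; the size depends on counts that the documents do not give and may be zero.

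This should be corrected because it bears on a primary endpoint in the final report. It does not call any escalation decision or the MTD determination into question.

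**What to change.** Add a DLT-evaluable population to SAP Section 3.5: Part 1 patients judged evaluable for Cycle 1 DLT under Section 3.6.2, as decided by the CRC. In Section 4.7.1, name it as the denominator of the DLT table. Show the number dosed, number evaluable, number with DLT and percentage, by dose level and, if more than one was used, by dosing schedule. Put any DLT in a dosed but non-evaluable patient on its own line. Keep the Safety Population for every other adverse event table.

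The cost is one population flag and one table denominator. The SAP says the data were collected on eCRFs. If evaluability is not recorded there, the flag must be taken from the CRC minutes, which the protocol requires. Basing it on those decisions also avoids programming from Section 3.6.2 alone. That section first speaks of receiving at least 80% of doses and later of missing more than 80% because of toxicity, and the two statements should be reconciled. Reported DLT percentages may be slightly less favourable.

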2.4 Primary end-points

The primary end-points of this study are:

- Ongoing evaluation of Adverse Events (AEs) during treatment and follow up; evaluation of dose limiting toxicity (DLT) during Cycle 1
- Safety, pharmacokinetic (PK), pharmacodynamic (PharmD) and tumour response assessments

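### The SAP's DLT table runs on the Safety Population, so patients dosed and then replaced as not DLT-evaluable stay in its denominator

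*SAP*

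**What the plan says.** SAP 2.4 makes "evaluation of dose limiting toxicity (DLT) during Cycle 1" part of the primary endpoint. SAP 4.7.1 lists a DLT table by system organ class and preferred term among the adverse event tables and gives it no population of its own. It therefore falls under the general rule in SAP 4.7: "All safety analysis will be performed on Safety Population".

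SAP 3.5 defines three sets: enrolled patients, the Efficacy Population and the Safety Population. The Safety Population is "All patients who receive at least one dose of study drug". By default, under SAP 4.1, "the denominator for percentages will be the number of patients in a given dose level within the analysis population of interest", and "All summary tables will include the analysis set sample size".

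SAP 3.6.2 says that in Part 1 "patients will be replaced if they are not considered evaluable for DLT during Cycle 1". As a general rule a patient is evaluable with 12 of 15 planned doses, or with fewer if the shortfall is due to ALM201-related toxicity. The CRC reviews evaluability case by case. No analysis set, table or denominator in the SAP uses this status.

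**The concern.** A DLT percentage is meant to describe patients who were observed well enough in Cycle 1 for a DLT to be ruled in or out. A patient replaced for missing too many doses was not observed to that standard. Leaving that patient in the denominator treats an unknown outcome as a DLT-free one, so the error can only lower a non-zero rate.

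The SAP avoids this problem for tumour response: its Efficacy Population is "All patients with at least one post-baseline tumour response assessment", and the response summary in SAP 4.5 has a row for patients who are not evaluable. It makes no equivalent provision for DLT.

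What is at stake is the final Part 1 report, which is the whole purpose of this SAP. Its readers will use the DLT counts by dose, and the N beside them, to judge tolerability.

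**Working it through.** **1. The plan's own figure.** Dosing on Days 1–5, 8–12 and 15–19 gives 5 + 5 + 5 = 15 doses, and 0.80 × 15 = 12. This reproduces the 12 of 15 in SAP 3.6.2.

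**2. Which patients enter the denominator.** Let n be the DLT-evaluable patients at a dose and k the patients dosed there and then replaced. SAP 3.5, 4.1 and 4.7 together give a denominator of n + k. The evaluability rule in SAP 3.6.2 implies n. Patients replaced before any dose do not count in either.

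**3. Effect on the printed percentage, x/(n + k).** The documents do not give k, so 0 to 3 is assumed.

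| DLTs among evaluable | k = 0 | k = 1 | k = 2 | k = 3 |
|---|---|---|---|---|
| 1 of 3 | 33.3% | 25.0% | 20.0% | 16.7% |
| 1 of 6 | 16.7% | 14.3% | 12.5% | 11.1% |
| 2 of 6 | 33.3% | 28.6% | 25.0% | 22.2% |

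One replaced patient shifts these by 8.3, 2.4 and 4.8 percentage points. Under the protocol synopsis (Dose Limiting Toxicity) a first DLT leads to expansion to as many as six patients, so the six-patient rows are the likelier final results.

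**4. Zero DLTs.** The percentage is 0% whatever the denominator, but N carries the information. The two-sided 95% exact upper limit is 1 − 0.025^(1/N): 45.9% for 0/6, 41.0% for 0/7 and 36.9% for 0/8. For 0/3 it is 70.8% and for 0/4 it is 60.2%. The SAP plans no such interval; these figures only show how much extra evidence the larger N would appear to give.

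**5. How often a non-zero percentage would be changed.** Assume independent patients, a chance q that a dosed patient is non-evaluable, and a DLT rate p.
- At least one replacement while reaching six evaluable patients has probability 1 − (1 − q)^6, which is 0.265, 0.469 and 0.738 for q = 5%, 10% and 20%.
- At least one DLT in the first three has probability 1 − (1 − p)^3, which is 0.271 for p = 10% and 0.488 for p = 20%.
- The product is roughly the chance that a given dose has both, if every such cohort fills to six: 7%, 13% and 20% for p = 10%, and 13%, 23% and 36% for p = 20%.

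**6. Whether a reader could recover n.** SAP 3.6.2 gives the example that missing one dose a week may be acceptable while missing three in a row is not. Both patients received 15 − 3 = 12 doses, exactly 80%, so counting doses in the exposure listing cannot separate them. The disposition summary in SAP 4.2 has no row for DLT-evaluable or replaced patients, and no planned output shows the CRC's decisions.

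**The case against.** The best defence is that this is one descriptive table in a phase 1 report. The DLT count is printed whatever the denominator. Exposure is listed, and patients dosed at each cycle and reasons for discontinuation are reported. The shift is a few percentage points, and a percentage changes only where a dose has both a DLT and a replaced patient. All of that is true, and it limits the size of the point. It does not remove it. The printed N is still wrong for this endpoint, and step 6 shows that the listings do not let a reader correct it.

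Four stronger readings are tempting, and the documents do not support them.
- A reader might infer that escalation or the maximum tolerated dose was affected. The synopsis gives those decisions to the CRC, on evaluable patients.
- A reader might see conflicting evaluability rules, because the synopsis's Cohort Review Committee section omits the toxicity exception. That section says who is eligible without saying that nobody else is, and SAP 3.6.2 carries the exception. The phrase "misses more than 80% of their intended dose due to toxicity considered to be related to ALM201" may look like a slip. Read literally it means at least 13 of 15 doses missed, and sending that extreme case for review is consistent with the general rule.
- A reader might infer that 300 mg could be declared the maximum feasible dose on a single patient. That depends on protocol Sections 4.2 and 4.2.1 and the CRC Charter, which the public synopsis does not reproduce. The halt after Part 1 also leaves it without consequence for this trial.
- A reader might want exact confidence intervals added. The protocol plans no formal statistical analysis in dose escalation, so that is a preference and not a correction.

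**Conclusion.** The point holds as a reporting fault in the SAP. Its stated rules give the DLT table a denominator that includes patients the same SAP regards as unable to contribute a DLT assessment. This is more than missing detail, because the default in SAP 4.1 and 4.7 produces a definite and wrong number. In a six-patient cohort the dilution is about 2 to 5 percentage points for one replaced patient, and always downwards.

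The conclusion assumes that at least one dosed patient was replaced. If none was, every figure is unchanged. It also assumes that text outside the public synopsis and the available SAP does not name a DLT-evaluable set; nothing in the available text does. The plan is descriptive, so neither type I error nor power is involved. The change should be made because the endpoint is primary and the remedy is nearly free.

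**What to change.** Add to SAP 3.5:

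> DLT-evaluable Population: Part 1 patients confirmed by the CRC as evaluable for DLT in Cycle 1 under Section 3.6.2 (as a general rule at least 80% of planned doses, or fewer because of ALM201-related toxicity), plus any patient with a DLT.

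Membership must rest on the CRC's confirmation. A pure 80% count would keep a patient whom the CRC rejects at exactly 12 of 15 doses.

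Use this set as the denominator of the DLT table at each dose level, stated as an exception to SAP 4.7. Add rows for DLT-evaluable and replaced patients to the disposition summary in SAP 4.2, and list the CRC's evaluability decisions with reasons.

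The cost is one definition, one denominator, two rows and one listing. No new patient data are needed, only the CRC's evaluability decisions; the synopsis already requires CRC discussions to be minuted. The one drawback is that the DLT table will show a different N from the other adverse event tables and needs a footnote saying why.
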